11.3 Exclusion Criteria

Table 3 – Exclusion Criteria

Exclusion Criteria	Determinant
Subjects directly affiliated with the study or their immediate families (parent or sibling, whether by birth or legal adoption)	Physician interview
Subjects currently on concurrent medication listed as excluded on the Concomitant Medication list (Appendix D) and/or use of an investigational drug within 4 weeks of the baseline visit.	Physician evaluation and review of medical record
Active substance use	Urine drug test (at screening; second test allowed prior to randomization as permitted by Sponsor)
Prior TMS, vagus nerve stimulation (VNS), or ECT	Medical history
Contraindication to MRI (only for Structural Head MRI subset subjects)	Physician evaluation; medical history; MRI Safety Screening Questionnaire

Contraindication to TMS	Physician evaluation and review of
Conductive, ferromagnetic, or other magnetic-sensitive metals implanted in the subject's head within 30 cm of the treatment coil excluding the mouth that cannot safely be removed. Examples include cochlear implants, implanted electrodes/stimulators, aneurysm clips or coils, stents, bullet fragments, jewelry and hair barrettes.	medical record
Active or inactive implants (including device leads), including deep brain stimulators, cochlear implants, and vagus nerve stimulators.	
Cardiac pacemakers, implanted medication pumps, intracardiac lines	Physician evaluation and review of medical record
A true positive response to any question on the TASS questionnaire	Physician evaluation
History of neurological disorder or insult including but not limited to the following that may increase risk of seizure:	Physician evaluation and review of medical record
 Antecedent seizures Any condition likely to be associated with increased intracranial pressure Space occupying brain lesion History of cerebrovascular accident Transient ischemic attack within 2 years Cerebral aneurysm Dementia Brain surgery Head trauma with loss of consciousness for ≥5 minutes History of stroke History and/or family history of epilepsy Unstable medical conditions, including: Hematological or infectious (e.g., human immunodeficiency 	Physician evaluation; medical history
 virus-HIV) disorders. History of autoimmune, endocrine, viral, or vascular disorder Unstable cardiac disease, uncontrolled hypertension, or sleep apnea Current anticoagulant, immune suppressive, and/or chemotherapy or those who have received any of these therapies within 3 months before enrollment in the study. 	
Clinically significant laboratory abnormality, in the opinion of the Investigator	Physician review of screening laboratory tests
Individuals diagnosed with the following conditions (current unless otherwise stated):	M.I.N.I. or M.I.N.I. KID (age <18) to confirm DSM-5 criteria
 Depression secondary to a general medical condition, or substance induced: Seasonal pattern of depression as defined by DSM-5 Any psychotic disorder (lifetime), including history of schizophrenia, schizoaffective disorder, other psychosis, psychotic features in this or previous episodes, amnestic 	Physician Examination and conference with family member/guardian to confirm findings (age <18 or legal requirements of the state)

 disorder, Mental retardation, Substance dependence or abuse within the past year (except nicotine or caffeine), Bipolar disorder, Obsessive compulsive disorder (lifetime), Post-traumatic stress disorder (lifetime), Eating disorder (lifetime). Any psychiatric disorder, which in the judgement of the Investigator may hinder the subject in completing the procedures required by the study	M.I.N.I. KID (ages up to <18) or M.I.N.I. (ages \geq 18) to confirm
protocol. If participating in psychotherapy, must have been in stable treatment for at least 3 months prior to screening into the study with no anticipation of change in the frequency or focus of therapeutic sessions over the duration of the study.	Physician evaluation; medical history
 Significant acute suicide risk, defined as follows: Suicide attempt within the previous 6 months that required medical treatment; or History of attempt within the past 2 months or ≥2 suicide attempts in the past 12 months; or Has a clear cut plan for suicide and states that he/she cannot guarantee that he/she will inform a family member or call his/her psychiatrist or the investigator if the impulse to implement the plan becomes substantial during the study; or In the Investigator's opinion, is likely to attempt suicide within the next 6 months. 	Physician evaluation, M.I.N.I./M.I.N.IKID
Any other relevant medical, personality, or psychosocial issues specific to the subject that the PI determines to be reason for exclusion from the study	Physician evaluation; medical history
Pregnant or suspected pregnancy	Urine pregnancy test
If sexually active female, not on an accepted method of birth control. See Appendix D, Concomitant Medication List	
Inability to locate and quantify a motor threshold	Motor Threshold determination

11.4 Subject Recruitment, Enrollment and Screening

Subject Recruitment

Several resources will be utilized for recruitment of potential subjects including:

- from within the clinical and referral practices of the clinical study site
- referrals from other care providers within the treatment communities
- radio advertisements
- invitation letters sent to parents of potentially eligible subjects
- print advertisements, including but not limited to brochures, flyers, Craig's List, and listings in research classifieds
- trial listing with ClinicalTrials.gov

Page 31 of 61

- trial listing on university and clinical study site website
- social media

All advertising materials will be reviewed and approved by the site's IRB prior to use.

Potentially interested adolescents and their families may be provided with printed subject educational materials to aid them in making an informed decision regarding their willingness to participate in this study.

Subject Enrollment

At the time of the enrollment visit, potential subjects and their parent(s) will be provided with a written copy of the current IRB-approved informed consent/assent form from the site at which they will be receiving study treatments. All adolescents and their guardians will be provided a careful assent and consent discussion prior to enrollment. Due to the nature of a sham-controlled trial, all subjects will need to understand that during Phase I of the trial, they will be randomized to either the active treatment condition or the sham treatment condition. They will also be informed about the opportunity to receive open, active TMS treatment during Phase II if they did not receive protocol-defined clinical benefit during Phase I. For subjects who reach the age of maturity (18 years or legal requirements of the state) during their participation in the study, written consent will be obtained from the subject at the next visit following their birth date.

Subject Screening

Following the informed consent process, enrolled subjects will begin the study eligibility screening process. Verification of inclusion and exclusion will be completed by the study physician to ensure that the subject is eligible for the study and that it is safe for them to participate. Subjects must have discontinued all antidepressants and psychotropics for at least one week (or until all traces are eliminated from the subject's system) prior to administering the HAMD₂₄/MADRS and any other efficacy assessment.

11.5 Early Withdrawal of Subjects

When and How to Withdraw Subjects

Subjects may withdraw voluntarily from the study at any time. They may be withdrawn from the study by the Investigator if a subject:

- experiences a seizure,
- experiences a DSM-5-confirmed treatment-induced mania,
- is non-compliant with study procedures; or
- the randomization code is broken for this subject.

The Investigator may also withdraw a subject if he/she believes that for safety reasons it is in the best interest of the subject to be withdrawn.

Discontinuation information [e.g., date and the reason(s) for discontinuation] must be recorded in the subject's CRF (i.e., Study Completion Form). Subjects who discontinue prematurely should complete the Week 6 assessment procedures within 2 days following their last TMS treatment session. See the Schedule of Events for the specific procedures to be performed at this discontinuation visit.

Subjects withdrawn from the study due to an AE will be followed up for 30 days or until resolution. Subjects withdrawn from the study will not be replaced, regardless of the reason for withdrawal. An effort

Page 32 of 61

will be made to determine why a subject does not return for the required visits or is dropped from the study. This information will subsequently be recorded on the subject's CRF.

Subjects will be encouraged to remain compliant with all expected study visits. Non-adherence to expected study visits will be documented and may result in removal from the study. This will be clearly discussed during the consent/assent process and reinforced throughout the study through regular screening for issues with compliance.

12 Study Device

12.1 Description

The NeuroStar TMS Therapy[®] System is a computerized electromechanical instrument that produces and delivers brief duration, rapidly alternating (pulsed) magnetic fields to induce electrical currents in localized regions of the cerebral cortex. It is a non-invasive tool used for the treatment of subjects with MDD who have not achieved sufficient clinical benefit from antidepressant pharmacotherapy. The NeuroStar TMS Therapy System has been FDA-cleared for use in adult subjects. NeuroStar XPLOR[®] is a clinical research option for the NeuroStar TMS Therapy System that provides features necessary to conduct randomized controlled trials and other TMS research. The active treatment modality is essentially the same for both the NeuroStar TMS Therapy System and NeuroStar XPLOR.

The NeuroStar XPLOR TMS System consists of the following equipment and software:

- Mobile Console (includes processor module, power module, mast, gantry, halo, and display arm)
- System Software; the XPLOR option also includes a dedicated system software application (software version 1.7.5 or greater) with its own dedicated database of subject treatment history, TMS TrakStar[®] application, and TrakStar database that operates only with the corresponding XPLOR Software, maintaining isolation, security, and data integrity of the research.
- TMS TrakStar[®] Data Management System software
- Therapy Coils included with the XPLOR option is a set of three TMS coils:
 - a blinded sham or placebo coil; the sham coil is acoustically matched to protect the integrity of the blind,
 - \circ a blinded active coil, and
 - a standard treatment coil that can be used for performing motor threshold level determination or open-label treatment.
- Head Support System (includes laser positioning aid and coil positioning guide)
- Treatment Chair
- Positioning Cushions (to enhance comfort and positioning of the subject in the required posture for the duration of the treatment session)

The NeuroStar TMS Therapy System also requires supplies and disposables for each treatment session:

- Head Cushion Liner
- Head Side Pad Liner
- Head Positioning Straps
- Earplugs
- SenStar[®] Treatment Link (a single-use medical device)
- Used SenStar Treatment Link Return box

12.2 Subject Identification

Each subject will be assigned a unique subject identification upon signing the informed consent form. This number will consist of an assigned 2-digit study site identifier, and a unique, 3-digit subject identifier. For example, the first subject screened at site 01 would be subject 01-001.

Subjects should be identified to the Sponsor only by their assigned number and initials except where requested on the CRFs and source documents. The Investigator must maintain a master list linking subject names and the identifying information indicated above.

12.3 Randomization

A randomization schedule will be generated by Neuronetics or a designated contract research organization. Subjects will not be randomized until all entry (inclusion and exclusion) criteria have been met and all pre-study procedures have been satisfactorily completed. Eligible subjects will be randomly assigned to receive one of the two treatment regimens (active TMS treatment or sham TMS treatment), and the next available randomization number for the subject's stratum will be recorded in the screening log and on the subject's CRF. Randomization numbers may not be reassigned. A permuted-block procedure will be used to randomly assign the treatment conditions, with a fixed block size for each stratum.

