13.4 Blinding of Study

The blinded TMS coils will arrive from Neuronetics and will be identical in appearance and labeled generically (e.g., Coil X, Coil Y). The device will recognize one coil as active and the other coil as sham. Once a subject has been randomized, the device will "link" the subject's treatment with the corresponding coil. The device will remain inactive if the "incorrect" coil is used for a subject, adding an additional safeguard for each subject and the integrity of the study and allowing the study treaters to remain blinded to the nature of the subject's treatment assignment.

Subjects will be randomly assigned to a coil and will receive all treatments during Phase I of the trial using this coil. Neither the subject nor the study staff (including those administering TMS treatments and those administering mood, cognitive, safety, and imaging assessments) will know whether the subject is

Page 35 of 61

receiving active or sham treatment. Subjects and Parents (if subject < 18 years old or does not meet the local or state legal age requirement) will complete a Pre/Post-Treatment Expectations and Experience Questionnaire (PRE-TEEQ-A/PRE-TEEQ-P and POST-TEEQ-A/POST-TEEQ-P) that queries their initial expectations of trial outcome and final impression of the trial.

In Phase II and III, all treatments will be provided with the known-active coil.

To minimize any source of bias, unblinding of the study will not be done until all subjects have completed all study phases. However, unblinding will occur if the Data and Safety Monitoring Board, consistent with their assigned charter and associated stopping rules, determines that it necessary to do so.

As an additional measure to ensure the integrity of the blinded coil assignment, the study coils at each location may be retrieved by Neuronetics study personnel and new study coils re-assigned.

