15.2 Analysis Plan

This study in adolescent patients is a randomized, parallel-group comparison of treatment with TMS as compared to a sham control. It will be conducted at approximately 16 sites in the United States and Canada, with independent randomization protocols within each site, using a permuted block design to improve balance within site. The primary outcome is the last post-treatment symptom score (LV) measured using the primary efficacy outcome measure (efficacy variable and point of declaration are blinded to the Investigator) for each subject. The analysis will be performed on the strict intention-to-treat sample of all evaluable subjects, meaning those subjects with a baseline and at least one post-baseline observation available for analysis.

Page 40 of 61

Poorly recruiting sites, defined as those with fewer than 2 randomization blocks, will be pooled into one or more pseudo-sites for purposes of analysis. To ensure that nearly all sites will be of adequate size we will adopt a strict closure policy for sites that do not show early signs of enrollment success. With 16 sites, the average number of subjects per site is approximately 18, so there may be a few sites with fewer than 2 randomization blocks. A site that has not randomized at least 2 subjects in the first quarter of their enrollment may be closed. Then if as many as 2 sites are closed, and one poorly performing site eludes closure, there will be no more than one pseudo-site comprising a total of no more than 2 subjects from the closed site and approximately 11 from the poorly performing site, or no more than 13 subjects in all (i.e. <5% of the total sample).

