#### A. Trial Design Summary:

Study 44-02219-000 is a multi-center, randomized, sham-controlled clinical trial evaluating the safety and effectiveness of treatment with the NeuroStar TMS Therapy system in adolescent patients ages 12 through 21 who have failed to received treatment benefit from prior administration of antidepressant medications. The study is organized into 3 separate phases. During Phase I, patients meeting inclusion and exclusion criteria are randomly assigned in a 1:1 ratio to receive either daily treatment with the NeuroStar TMS Therapy device in the XPLOR research configuration or sham NeuroStar treatment for up to 6 weeks (30 treatments). Patients who do not meet criteria for clinically significant treatment benefit are offered the opportunity to enter Phase II, where open-label active NeuroStar TMS Therapy is provided to all patients for up to 6 weeks (30 treatments). Patients who receive clinically significant treatment benefit at the conclusion of either Phase I or Phase II are offered the opportunity to proceed into Phase III, where NeuroStar TMS Therapy is tapered, and patients are continually monitored for up to 6 months to determine the durability of effect of benefit from the acute treatment phases of the study. All patients are treated with NeuroStar TMS Therapy as a monotherapy, no antidepressant medications are permitted during the course of all three study Phases. During Phase III, patients are permitted to receive a reintroduction of an acute course of NeuroStar TMS Therapy if they meet protocol-defined criteria for symptom re-emergence.

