#### **D.** Center Pooling Methods:

The distribution of patient sample sizes across study sites will be inspected at completion of enrollment. In order to permit a meaningful evaluation of between site variance in the statistical analyses of efficacy outcome, sites with small numbers of patients may be pooled to form a single pseudo-site for purposes of statistical analysis. If a site did not randomize at least one randomization block (6 subjects), they will be combined for 1 pseudo-site.

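### Fixed blocks of six within site, combined with visible coil letters, could let a site that works out the block size foresee up to a quarter of coil-letter assignments

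*Protocol*

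**What the plan says.** Protocol 12.3 (Randomization) states that "A permuted-block procedure will be used to randomly assign the treatment conditions, with a fixed block size for each stratum". It does not say what the strata are. Protocol 15.2 describes schedules "with independent randomization protocols within each site, using a permuted block design to improve balance within site". SAP Section 1.A says patients are "randomly assigned in a 1:1 ratio". The number 6 appears in SAP Section 3.D: "If a site did not randomize at least one randomization block (6 subjects), they will be combined for 1 pseudo-site". SAP Section 2.B says that the SAP was not shared with the sites.

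Protocol 13.4 (Blinding of Study) says the two blinded coils "will be identical in appearance and labeled generically (e.g., Coil X, Coil Y"). The device treats one coil as active and the other as sham, and will not run with the wrong coil for a subject. It adds: "Subjects will be randomly assigned to a coil and will receive all treatments during Phase I of the trial using this coil". The sponsor may retrieve and re-assign coils, but no trigger or schedule is given.

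**The concern.** In most masked trials a fixed block size does little harm, because staff cannot see past allocations and so cannot count down a block. That protection is weaker here. Treating staff must use the coil to which the subject is linked, so they see which of two groups every earlier subject at the site belongs to. With a known block of six in a 1:1 ratio, once three subjects have had one letter the rest of the block must have the other.

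Eligibility is settled before randomisation, on clinician ratings (HAMD24 and CGI-S thresholds, and the change between screening and baseline) and on open investigator judgement (Protocol 11.1 and 11.3). Neither 12.3 nor 13.4 requires the staff who judge eligibility to be different people from those who handle coils. If a person judging entry could foresee the next group, borderline candidates could be admitted, delayed or declined accordingly. The primary analysis adjusts for baseline score and medication resistance level, but not for unmeasured prognosis. The adult effects quoted in the plan are only 1.7 to 2.5 HAMD24 points, so a modest bias would matter.

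**Working it through.** The documents state no predictability figure, so there is none to reproduce.

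**Inputs.** Block of 6 (SAP 3.D); 1:1, so 3 of each letter per block (SAP 1.A); separate schedules by site (Protocol 15.2); 100 subjects (Protocol Section 7) over about 16 sites (Protocol 15.2), or 100/16 = 6.25 per site. Protocol 15.2 instead gives an average of about 18 per site, but 16 × 18 = 288, which does not match 100.

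**Could a site infer 6?** Protocol 15.2 defines a poorly recruiting site as one with less than two blocks and puts such a site at about 11 subjects. If 11 is the largest such site, 2b − 1 = 11 and b = 6, in agreement with the SAP. This is a hint, not a disclosure.

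**Certain assignments in a completed block.** There are C(6,3) = 20 equally likely sequences. An assignment is certain once one letter is used up.
- Places 1 to 3: 0
- Place 4: first three alike, 2/20 = 0.10
- Place 5: first four split 3 and 1, 8/20 = 0.40
- Place 6: always, 1.00

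The sum is 1.5 of 6 = 25%. The closed form for a block of 2m agrees: 2m/(m + 1) = 6/4 = 1.5.

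**Best guess.** Guessing the letter with more places left is right with probability 0.5, 0.6, 0.6, 0.7, 0.7 and 1.0 by place. The sum is 4.1 of 6 = 68.3%, against 50% by chance.

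**Whole trial.** Incomplete blocks lower the share.
- Even sites (12 of 6 and 4 of 7): 16 × 1.5 = 24 of 100, or 24%.
- Sites filling at random (simulated, equal or unequal recruitment rates): about 17%.
- Two further strata within each site (an assumption): about 7 to 11%. Three: about 3 to 7%.

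**From letter to arm.** Protocol Table 1 gives application site pain of 35.8% active and 3.8% sham in the adult trial. At the last place in a block, two or three earlier subjects have had active treatment. At the adult rate, the chance that at least one reports such pain is 1 − 0.642² = 59% or 1 − 0.642³ = 74%. For two or three sham subjects it is 1 − 0.962² = 7% or 1 − 0.962³ = 11%. Separately, an emergency envelope opened under Protocol 12.4 shows one subject's arm, and hence what that letter means at that site until coils are re-assigned.

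**Varying the block size.** Simulated for an observer who knows the set of sizes but not their order, with sizes drawn equally. Ranges cover 6, 12 and 18 subjects per site.

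| Block sizes | Certain | Best guess correct |
|---|---|---|
| Fixed 6 (exact) | 25% | 68.3% |
| 2, 4, 6 | 2.8 to 3.7% | 68.6 to 69.6% |
| 4, 6 | 5.6 to 7.6% | 67.3 to 68.4% |
| 4, 6, 8 | 1.0 to 2.4% | 64.7 to 67.0% |

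**The case against.** The strongest reply is that several things must go wrong together. A site must know the block size, track the sequence, and decode the letter. The figure 6 is stated only in the SAP, which sites did not see. A site that fills about one block cannot learn the size from its own sequence, since three of one letter also fits blocks of 8 or 10. The decoding clue is noisy, comes from adults, and appears only after earlier subjects have been treated. Coil re-assignment with new letters in mid-block would break the sequence. No passage says that entry raters see the letters.

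Most of this stands, and it limits the size of the point. A reader might infer that a quarter of treatment assignments are known in advance, or that about 25 of the 100 are exposed. The documents do not support either. What can be foreseen is a letter, and 25% is a ceiling for completed blocks with the size known.

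The reply does not remove the weakness. The site-facing protocol itself says the size is fixed and gives the hint from which 6 can be worked out. Coil re-assignment is optional and unscheduled. Separation of raters from treaters is not required. Completing eligibility before randomisation gives no protection when it is the next subject's letter that can be foreseen.

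**Conclusion.** The plan has an avoidable weakness in allocation concealment, worth correcting but not shown to have caused harm. If a site knows that blocks are of six, up to 25% of its coil letters are certain beforehand, or about 17 to 24% across 100 subjects and 16 sites. This assumes that site is the only stratum. SAP Section 3.G sets three age brackets for recruitment, and the analysis model uses two resistance levels, but neither is said to be a randomisation stratum. If either were, the share would be lower.

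Turning a foreseen letter into a foreseen arm needs the further, plausible but unproven, step of working out which letter is active. A reader might also infer that selection bias took place; nothing in the documents shows that. Nor would varying the block size stop guessing: the gain is that near-certainty goes, while best-guess accuracy changes by only a few percentage points.

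**What to change.** For subjects not yet randomised:
- Use permuted blocks within site whose sizes vary at random and are not disclosed. Avoid blocks of 2, which make guessing slightly easier than now; 4, 6 and 8 is a suitable set.
- Remove the statement in Protocol 12.3 that the block size is fixed, define the strata there, and keep the sizes only in the unblinded randomisation file.
- State the site-pooling rule as a number of subjects. This also removes a mismatch: Protocol 15.2 and SAP 2.B pool sites with less than two blocks, while SAP 3.D pools those with less than one.

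The cost is a new list, a few wording changes, and slightly more possible imbalance within small sites (at most 4 within a block of 8, against 3 within a block of 6).

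The SAP (Rev C, January 2019) describes some conduct in the past tense, so few or no subjects may remain. If enrolment is complete, pre-specify before unblinding a sensitivity analysis that repeats the primary model without the forced end-of-block assignments, and tabulate baseline HAMD24 by place in the block. Dropping 17 to 24 of 100 subjects would widen the standard error by about √(100/83) = 1.10 to √(100/76) = 1.15, so this checks the direction and size of the estimate and is not a second test of efficacy.
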